4.2.8 Analyses of Safety

All safety variables will be summarized for patients in the SP using descriptive statistical methods stratified by treatment regimen and cirrhosis status and overall.

An overview of tables for the individual values is given in Table 11.

The layouts of the tables mentioned above are provided in Part II of the SAP (Table Shells).

4.2.8.1 *Exposure to Study Medication*

One table will show the frequencies for early discontinuation and exceedance of ABBVIE regimen or ribavirin and the corresponding reasons for SP by treatment regimen and cirrhosis status. The ABBVIE regimen is considered to have been prematurely discontinued if actual duration is shortened for more than 7 days. The duration for taking ABBVIE regimen is considered to have been exceeded if the actual duration is prolonged for more than 7 days. Furthermore, summary statistics will be generated for the duration of ABBVIE regimen taken and the duration of ribavirin taken, i.e. n, mean, median, standard deviation [SD], minimum, maximum.

Unintended medication errors, i.e. patient missed taking Paritaprevir/r-Ombitasvir or Dasabuvir for at least 7 days in a row, will be displayed by medication for the entire treatment period.

4.2.8.2 *Co-medication*

Treatments, surgical and medical procedures will be coded by ABBVIE assigning appropriate preferred and class terms. Frequencies will be displayed for SP by treatment regimen and cirrhosis status.

In one table, the co-medication (preferred term) will be grouped by class. Only co-medication received during treatment specified by ABBVIE regimen will be displayed (Treatment profiles: A1, A2, C1 Drug B, C2 Drug B, C3 Drug B, D).

In another table, the co-medication (preferred term) will be grouped by profile. All treatment profiles will be considered, i.e.:

- A1: Continued (A1)
- A2: Permanently discontinued during CHC treatment (A2)
- A3: Permanently discontinued prior to CHC treatment (A3)
- B: Discontinued prior to CHC treatment and reintroduced post-treatment (B)
- C1 Drug A: Permanently replaced at start of CHC treatment (C1A)
- C1 Drug B: Substitute at start of CHC treatment and discontinued during CHC treatment (C1B)
- C2 Drug A: Permanently replaced at start of CHC treatment (C2A)
- C2 Drug B: Substitute at start of CHC treatment and continued (C2B)
- C3 Drug A: Replaced during CHC treatment (C3A)
- C3 Drug B: Substitute during CHC treatment (C3B)
- D: Introduced during CHC treatment (D)
- No profile reported: No profile reported

Another table will show the associated treatment profiles for the medications of special interest. Therefore the medication will be pooled appropriately. All treatment profiles will be considered.

A further table will show the associated treated conditions, i.e.:

- Alcoholic liver disease
- Angina pectoris
- Auto-immune hepatitis
- Auto-immune skin disease

- Bipolar disorder
- Chronic kidney disease
- Cryoglobulinemia
- Depression
- Diabetes mellitus (Type 1)
- Diabetes mellitus (Type 2)
- Hemophilia
- Hepatitis B
- Hepatocellular carcinoma
- HIV
- Hypertension
- Hyperthyroidism
- Hypothyroidism
- Immunologically mediated disease
- Insulin resistance
- Kidney transplantation
- Lipid disorder
- Liver transplantation
- Metabolic syndrome
- Myocardial infarction
- Opiate substitution
- Personality disorder
- Porphyria cutanea tarda (PCT)
- Primary biliary cirrhosis
- Schistosomiasis
- Schizophrenia
- Sickle cell anemia
- Steatosis (non-alcoholic)
- Stroke
- Thalassemia
- Tuberculosis
- v. Willebrand disease
- Wilson disease
- Other

All treatment profiles will be considered.

One table will displays the number of patients taking herbals except St. John's Wort, homeopathics or other drugs for which neither a name nor a profile nor a treated condition had to be reported. These medications will be excluded from the other co-medication tables.

A glossary will show the verbatim terms and the corresponding coded terms used (see Table 11).

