#### **9.4.1.5 Concomitant Medication**

**Concomitant medication** - the following will be documented:

- Concomitant medication used from the time when the decision is made to initiate treatment with the ABBVIE REGIMEN until after the last dose

It should be verified by the treating physician that concomitant medication can be safely administered with the ABBVIE REGIMEN (including ritonavir) and RBV. Some medications may be contra-indicated, some may require dose adjustments due to potential for drug-drug interactions (DDIs). The investigator or qualified designee should review the concomitant medication(s) labels and screen concomitant medications at each visit for potential DDIs.

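### The by-class table of on-treatment co-medication leaves out profile C3 Drug A, the drugs that were replaced during treatment

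*SAP*

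**What the plan says.** SAP 4.2.8.2 (Co-medication) plans several tables for the safety population by treatment regimen and cirrhosis status. The first groups preferred terms by class. One sentence states its scope and, in brackets, the profile codes that put the scope into practice: only "co-medication received during treatment specified by ABBVIE regimen will be displayed (Treatment profiles: A1, A2, C1 Drug B, C2 Drug B, C3 Drug B", with D as the last code.

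The section then defines eleven named profiles. Three of the definitions matter most here:

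- "C3 Drug A: Replaced during CHC treatment (C3A") is not on the list.
- "C3 Drug B: Substitute during CHC treatment (C3B") is on the list.
- "A2: Permanently discontinued during CHC treatment (A2") is on the list.

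A second table groups the same preferred terms by profile and covers every profile. The tables for medications of special interest and for treated conditions also cover every profile. SAP Table 11 gives the by-class and by-profile tables the short names tcom and tcomp.

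Protocol 9.4.1.5 collects co-medication from the decision to treat until after the last dose, so C3 Drug A entries will be in the data. It also asks sites to check co-medication for interactions at each visit: "Some medications may be contra-indicated, some may require dose adjustments due to potential for drug-drug interactions (DDIs").

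**The concern.** The list of codes does not match the scope it is meant to apply. A drug that was replaced while the patient was on treatment had been taken on treatment up to that point. The table shows its substitute but not the drug itself.

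What is at stake is the description of co-exposure. A drug stopped part-way through treatment with no successor falls under A2 and is counted. The same drug stopped at the same time but followed by a substitute falls under C3 Drug A and is dropped. Whether a successor was prescribed has no bearing on whether the first drug was received alongside the regimen. SAP 4.1.2 names concomitant medication among the secondary variables, and the protocol treats interactions as something to watch throughout treatment, so the table should count what it says it counts.

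**Working it through.** The plan states no figure to reproduce here. The check is to class each named profile by its own definition and compare the result with the list.

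| Profile | Timing under the SAP definition | Taken during treatment? | On the tcom list? |
|---|---|---|---|
| A1 | continued | yes | yes |
| A2 | stopped for good during treatment | yes, in part | yes |
| A3 | stopped for good before treatment | no | no |
| B | stopped before, resumed after | no | no |
| C1 Drug A | replaced at the start | no | no |
| C1 Drug B | substitute from the start, stopped during treatment | yes, in part | yes |
| C2 Drug A | replaced at the start | no | no |
| C2 Drug B | substitute from the start, continued | yes | yes |
| C3 Drug A | replaced during treatment | yes, in part | **no** |
| C3 Drug B | substitute during treatment | yes, in part | yes |
| D | introduced during treatment | yes, in part | yes |

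By definition 7 of the 11 profiles are on-treatment, and the SAP lists 6: 7 − 6 = 1. The missing one is C3 Drug A. The other four omissions (A3, B, C1 Drug A, C2 Drug A) fit the table's scope.

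Two features of the SAP's wording rule out timing as a reason for the omission. First, it separates replacement at the start from replacement during treatment: compare "C1 Drug A: Permanently replaced at start of CHC treatment (C1A") with the C3 Drug A definition quoted above. Second, exposure for only part of the treatment period is enough to qualify, because A2 and C1 Drug B are both listed.

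**What the omission does to each count, patient by patient**

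- Preferred term of the replaced drug: one patient too few, unless that patient has the same term under a listed profile (for example, if the substitute codes to the same term).
- Class of the replaced drug: one patient too few only if the patient has no listed drug in that class. A substitute from the same class is enough to keep the class count right.
- Patients with any co-medication: unchanged, because C3 Drug B keeps the patient in the table.

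**Size per affected patient**

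The only input is the expected enrolment of 50-55 (protocol 9.5, SAP 3.2). I assume that all of these patients are dosed and so enter the safety population.

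- 1/55 = 1.8 percentage points.
- 1/50 = 2.0 percentage points.

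This applies to the overall column. In a regimen-by-cirrhosis column the denominator is smaller and the step larger. The documents give no column sizes, so, as an assumption only, 10 patients would make the step 1/10 = 10 points.

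The total effect is the number of affected patients times this step. The documents give no frequency for C3 Drug A, so the total cannot be computed, and it could be zero.

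**The case against.** The strongest case on the other side is that little is lost. The by-profile table uses the same population and the same strata as the by-class table and shows C3 Drug A as its own category. The special-interest and treated-condition tables also cover all profiles. Someone asking which drugs were taken with the regimen and then replaced would find them there, labelled as replaced, and that is more informative for interactions than a count by class. All of this stands. It limits the consequence but does not make tcom agree with its own scope. Nor can a reader simply add the C3 Drug A rows to tcom, because a patient may have the same preferred term under two profiles and would be counted twice.

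Some stronger readings are tempting, and the documents do not support them:

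- **That co-exposure to replaced drugs disappears from the report.** It does not, for the reasons just given. The SAP does not designate tcom as its principal co-medication table.
- **That every patient with a C3 replacement is miscounted, or that the class total is too low whenever the substitute is of another class.** Both depend on what else the patient has under a listed profile.
- **That C3 replacements are the result of interaction screening.** Protocol 9.4.1.5 asks for the screening, but neither document says why a drug is replaced during treatment. Some switches may have unrelated reasons.
- **That a specific loss in percentage points can be claimed.** Only the step per patient can be given.

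It may also be said that adding one code would not make the table complete, since entries with no profile reported are outside the list too. That is true, but their timing is unknown, so leaving them out does not contradict the stated scope in the same way. It is a separate question.

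**Conclusion.** The point holds as an internal inconsistency in SAP 4.2.8.2. The by-class table is restricted to co-medication taken during treatment, and C3 Drug A is the only profile that meets this restriction by definition but is missing from the list. The SAP gives no reason for leaving it out.

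The consequence is small and conditional: a possible undercount at preferred-term level, and sometimes at class level, in one descriptive safety table. The size per patient given above rests on the expected enrolment and on all enrolled patients being dosed; how many patients are affected is unknown. Nothing in the SVR12, other effectiveness, adherence or adverse-event analyses depends on this list. It is a minor correction, but a clear one.

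**What to change.** In SAP 4.2.8.2, change the profile list for the by-class table to: A1, A2, C1 Drug B, C2 Drug B, **C3 Drug A**, C3 Drug B, D. Make the same change in the program for tcom. Leave the by-profile, special-interest and treated-condition tables as they are, since they already cover all profiles.

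The cost is one code added to a filter in the SAP text and in the table program. No new data are needed, because the profile is already recorded.

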4.2.8.3 Adverse Events

All tolerability variables will be summarized using descriptive statistical methods for the SP stratified by treatment regimen and cirrhosis status and overall.

AEs will be coded using MedDRA. A glossary will show the verbatim terms and the corresponding coded terms used (see Table 11).

The number and percentage of patients with treatment-emergent AEs (i.e. any reported event that begins or worsens in severity after initiation of study drug through 30 days post-study drug dosing including those who are related to the study drug independent of the occurrence and those where the date of onset is missing) will be tabulated by primary MedDRA SOC and PT.

Corresponding summary tables will be provided for all serious treatment-emergent AEs and additional for all non-serious treatment-emergent AEs. In the table of non-serious AEs (that must exclude any SAE) only preferred terms that occurred at a frequency of $\geq 5\%$ in any treatment group will be displayed (no SOCs will be displayed).

The tabulation of the number of patients with treatment-emergent AEs by severity (AEs by severity [mild, moderate, severe], AEs leading to death, AEs leading to hospitalization) and relationship to study drug will also be provided (ABBVIE regimen, ribavirin, medication error - paritaprevir/r-ombitasvir, medication error – dasabuvir, ABBVIE regimen withdrawn, ribavirin withdrawn).

Patients reporting more than one AE for a given MedDRA PT will be counted only once for that term using the most severe incident for the severity summary table and the most related for the relationship summary table. Patients reporting more than one type of event within a SOC will be counted only once for that SOC.

The frequency of pregnancies will be displayed as well.

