**Confidential Information**

**No use or disclose outside AbbVie is permitted without prior written authorization from AbbVie**

The Netherlands v 1.4 (26 March 2018). Protocol based on AbbVie shell protocol version 3.0 (22 April 2015) Page 11 of 65

≥50 IU/mL at the last measurement or (iii) had HCV RNA <50 IU/mL at the last measurement, but no HCV RNA measurement ≥70 days after the last actual dose of the ABBVIE REGIMEN due to reasons related to safety (e.g. dropped out due to adverse event) or incomplete efficacy information (e.g. virologic failure such as relapse is reported in the electronic case report form (eCRF) but date and value of the corresponding HCV RNA test is missing). The safety population (SP) is defined as all patients who received at least one dose of the ABBVIE REGIMEN.

Descriptive and exploratory statistical methods will be used to analyze the data of the study. All baseline and disease characteristics will be summarized for the CP stratified by the CP analysis groups (based on genotype 1 subtype, fibrosis status, treatment experienced or naïve), which are relevant for scheduled treatment combination ( $\pm$  dasabuvir,  $\pm$  RBV) and duration (12 or 24 weeks). In addition, baseline summaries will be repeated for the SP and TP without stratification into subgroups. Further details of analysis populations and the CP analysis groups will be specified in the statistical analysis plan (SAP).

The primary effectiveness analysis will be performed for CP patients, stratified by the CP analysis groups. Response rates (i.e. SVR12 rate, end of treatment [EoT] response rate, relapse rate, viral breakthrough) will be determined for the various CP analysis groups. The relapse rates will be estimated in patients of the CP analysis groups with EoT response and sufficient HCV RNA measurements post treatment. Viral breakthrough rates will be estimated in all patients of the CP analysis groups, who have at least one undetectable HCV RNA measurement on treatment and at least one on-treatment or EoT measurement thereafter. For all rates specified above 95%-confidence intervals (CIs) will be determined using the Wilson's Score method.

All safety variables will be summarized for patients in the SP using descriptive statistical methods stratified by the type of combination treatment and scheduled treatment duration.

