**Table 1 - SVR12 rates in clinical trials:**

Population and treatment duration	Genotype	SVR12 ABBVIE REGIMEN + RBV	SVR12 ABBVIE REGIMEN alone
Non-cirrhotic, treatment-naïve (12 weeks)	1a	95-97% (SAPPHIRE-I, PEARL-IV)	90% (PEARL-IV)
	1b	98-99.5% (SAPPHIRE-I, PEARL-III)	99% (PEARL-III)
Non-cirrhotic, treatment-experienced (12 weeks)	1a	96% (SAPPHIRE-II)	n.a.
	1b	97% (SAPPHIRE-II, PEARL-II)	100% (PEARL-II)

Confidential Information

No use or disclose outside AbbVie is permitted without prior written authorization from AbbVie  
The Netherlands v 1.4 (26 March 2018). Protocol based on AbbVie shell protocol version 3.0 (22 April 2015) Page 17 of 65

These results suggest that the ABBVIE REGIMEN with RBV is the optimal regimen for genotype 1a infected patients, while patients with genotype 1b do not require RBV.

The TURQUOISE-II [60] study explored the efficacy of the ABBVIE REGIMEN in the traditionally most difficult-to-treat cirrhotic patients. This large study enrolled exclusively genotype 1 infected patients with cirrhosis, including treatment-naïve and treatment-experienced individuals. All patients received the ABBVIE REGIMEN with RBV and were randomized to 12 or 24 weeks of therapy. Overall 92% and 96% of patients achieved SVR following treatment for 12 or 24 weeks, respectively. Analysis of subgroups demonstrated that the small difference in SVR between treatment arms was due largely to the subgroup of genotype 1a treatment-experienced prior null responders treated for 12 weeks who achieved an SVR of 80%. This subgroup of patients achieved an SVR of 93% when treated for 24 weeks. Among genotype 1a infected patients, partial responders and relapsers had higher SVR rates than null responders in the 12 week treatment group, while similar SVR rates were seen among the null responders, partial responders and relapsers treated for 24 weeks, suggesting that the longer duration of 24 weeks is required only for cirrhotic genotype 1a null responders. SVR rates were very high across all subgroups in genotype 1b treatment-experienced patients treated for 12 and 24 weeks.

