### **9.7.6 Tolerability Analysis**

All tolerability variables will be summarized using descriptive statistical methods for the SP stratified by type of combination treatment and scheduled treatment duration.

All SAEs, non-serious AEs and pregnancy occurrences are to be reported for patients included in the study (see Section 11.0 and 9.2.3). AEs will be coded using MedDRA. The number and percentage of patients with treatment-emergent AEs (i.e. any reported event that begins or worsens in severity after initiation of study drug through 30 days post-study drug dosing) will be tabulated by primary MedDRA SOC and PT.

Corresponding summary tables will be provided for all serious treatment-emergent AEs. The tabulation of the number of patients with treatment-emergent AEs by severity and relationship to study drug will also be provided. Patients reporting more than one AE for a given MedDRA PT will be counted only once for that term using the most severe incident for the severity summary table and the most related for the relationship summary table. Patients reporting more than one type of event within a SOC will be counted only once for that SOC.

---

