For biopsy as assessment method the respective categories are defined as follows:

- “No cirrhosis” is defined by “No fibrosis”, “Mild/minimal fibrosis”, “Moderate fibrosis”
- “Transition to cirrhosis” is defined by “Advanced Fibrosis”
- “Cirrhosis” is defined by “Cirrhosis”.)

CP analysis groups and related treatment regimens

The CP analysis groups are defined according to the patient's fibrosis status and genotype/subtype. The standard summaries by CP analysis groups in the CP and CPSFU population are structured follows (is not specified otherwise):

- Total (regardless of cirrhosis status)
 - (1) Total (regardless of genotype)
 - (2) G1 (Total)
 - (3) G1a (including mixed subtypes and patients with unknown subtype)
 - (4) G1b
 - (5) G4 (non-G1)
- Patients with cirrhosis
 - (6) Total (regardless of genotype)
 - (7) G1 (Total)
 - (8) G1a (including mixed subtypes and patients with unknown subtype)
 - (9) G1b
 - (10) G4 (non-G1)
- Patients without cirrhosis
 - (11) Total (regardless of genotype)
 - (12) G1 (Total)
 - (13) G1a (including mixed subtypes and patients with unknown subtype)
 - (14) G1b
 - (15) G4 (non-G1)

SP analysis groups

The SP analysis groups are defined according to the treatment regimen and patient's fibrosis status. The standard summaries by SP groups in the safety population are as follows (if not specified otherwise):

- Total (regardless of cirrhosis status)
 - (1) Total
 - (2) 2DAA w/o RBV
 - (3) 2DAA + RBV
 - (4) 3DAA w/o RBV
 - (5) 3DAA + RBV
- Patients with cirrhosis
 - (6) Total
 - (7) 2DAA w/o RBV
 - (8) 2DAA + RBV
 - (9) 3DAA w/o RBV
 - (10) 3DAA + RBV
- Patients without cirrhosis
 - (11) Total
 - (12) 2DAA w/o RBV
 - (13) 2DAA + RBV
 - (14) 3DAA w/o RBV
 - (15) 3DAA + RBV
- Patients with unknown fibrosis status
 - (16) Total
 - (17) 2DAA w/o RBV
 - (18) 2DAA + RBV
 - (19) 3DAA w/o RBV
 - (20) 3DAA + RBV

(2DAA - paritaprevir/r-ombitasvir, 3 DAA - paritaprevir/r-ombitasvir + dasabuvir, RBV – ribavirin taken, w/o RBV – no ribavirin taken)

NCP analysis groups

The summary tables for the NCP will only show the data pooled for all patients in the NCP without any subgrouping by genotype and/or fibrosis status.

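### The SAP replaces the protocol's scheduled-duration stratum for tolerability with cirrhosis status, without declaring it, so cumulative adverse event percentages can mix 12- and 24-week courses

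*SAP*

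**What the plan says.** Protocol 9.7.6 reads: "All tolerability variables will be summarized using descriptive statistical methods for the SP stratified by type of combination treatment and scheduled treatment duration". The protocol abstract (Data Analysis) applies the same rule to all safety variables: "stratified by the type of combination treatment and scheduled treatment duration".

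The SAP uses another second factor. Section 4.2.8 has all safety variables "stratified by treatment regimen and cirrhosis status and overall", and 4.2.8.3 repeats this for adverse events: "All tolerability variables will be summarized using descriptive statistical methods for the SP stratified by treatment regimen and cirrhosis status and overall". Section 4.2.1 builds the tables on it: "The SP analysis groups are defined according to the treatment regimen and patient's fibrosis status". The 20 safety groups listed there are four regimens plus a total, each shown overall and for patients with cirrhosis, without cirrhosis and with unknown fibrosis status. None is split by 12 versus 24 weeks. Every adverse event table title in SAP Table 11 names regimen and cirrhosis status, and none names duration.

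The measure is the number and percentage of patients with a treatment-emergent event, defined as "any reported event that begins or worsens in severity after initiation of study drug through 30 days post-study drug dosing". The SAP also counts drug-related events whenever they occur and events with missing onset. It plans no rate per unit of patient-time.

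**The concern.** Describing tolerability is a secondary objective. A cumulative percentage grows with the time over which events are counted, so columns are comparable only if their observation times are similar. The protocol's strata secure that for the scheduled window; the SAP's do not.

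The substitute factor is also related to duration without identifying it. The protocol calls the core-population groups, which include fibrosis status, relevant to scheduled combination and duration (abstract and 9.7.2). Footnote c to its Table 2 makes the therapy initiated, including 12 or 24 weeks, depend on genotype and disease status. Its reading of the cirrhosis trial in 7.1 links the longer course to one cirrhotic subgroup: "suggesting that the longer duration of 24 weeks is required only for cirrhotic genotype 1a null responders". A cirrhotic column may therefore hold both courses beside a non-cirrhotic column that is mainly 12 weeks. A reader who saw a higher percentage under cirrhosis could take it as poorer tolerability when part of it is longer observation.

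**Working it through.** **1. Is the change declared?** The SAP states its departures elsewhere: the upper bound on the SVR12 window (4.1.1), the added 48-week windows (notes to Tables 2 and 3) and the replacement of shift tables (4.2.8.4, within the safety section). It makes no such statement for the safety strata. Protocol 9.7.6 leaves additional details of the adverse event analysis to the SAP; replacing a named stratum goes beyond that.

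**2. Scheduled observation window.** Inputs are the course lengths in protocol 9.2.2 and the 30-day tail in SAP 4.2.8.3. There is no planned figure for this window to reproduce.

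- 12 weeks: 12 × 7 + 30 = 114 days
- 24 weeks: 24 × 7 + 30 = 198 days
- Ratio: 198 / 114 = 1.74

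These are approximate. Protocol 9.4.1.1 allows enrolment up to 4 weeks into treatment. If event capture began only then, the windows would be 114 − 28 = 86 and 198 − 28 = 170 days, a ratio of 1.98.

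**3. Effect on a cumulative percentage.** Assume the same constant hazard in all patients (my assumption; the documents give no event rates). Then p24 = 1 − (1 − p12)^(198/114).

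| 12-week percentage | 24-week percentage |
|---|---|
| 5% | 8.5% |
| 10% | 16.7% |
| 20% | 32.1% |
| 30% | 46.2% |
| 50% | 70.0% |

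**4. Effect in a mixed cirrhotic column.** Let f be the share of cirrhotic patients on 24 weeks, with all non-cirrhotic patients on 12 weeks and a common 12-week percentage of 20%. The cirrhotic column shows (1 − f) × 20% + f × 32.1%.

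| f | Cirrhotic column | Ratio to non-cirrhotic 20% |
|---|---|---|
| 0 | 20.0% | 1.00 |
| 25% | 23.0% | 1.15 |
| 50% | 26.1% | 1.30 |
| 75% | 29.1% | 1.46 |
| 100% | 32.1% | 1.61 |

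If all events fall early in treatment, p24 equals p12 and every row returns to 20%.

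**5. Cell counts for 50-55 patients.**

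- Protocol scheme: 4 regimens × 2 durations = 8 cells, 50/8 to 55/8, about 6-7 patients each on average.
- SAP scheme without totals: 4 regimens × 3 fibrosis categories = 12 cells, about 4-5 each.
- All three factors crossed: 24 cells, about 2 each.

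**The case against.** The best defence is that this is a descriptive secondary analysis with no planned between-group comparison of adverse events, and that the SAP is not silent on duration. Section 4.2.8.1 summarises the duration of treatment taken, and Table 11 lists that output by the same regimen and cirrhosis groups as the event tables, so a reader can see which columns had longer exposure. That is a real mitigation, but it does not adjust the event percentages or separate the two courses within a column.

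The size may also be small. The protocol's background confines the need for 24 weeks to a narrow subgroup, and the local label and the number of 24-week patients are not in the documents. A constant hazard fits some events poorly: protocol 7.1 describes bilirubin elevations that peaked by Week 1 and generally resolved. This stands, and it is why the result is given as a range starting at zero.

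If the 24-week patients are mostly cirrhotic, the protocol's strata would confound duration with cirrhosis in the other direction. That also stands; neither set of tables alone separates the two factors.

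Sparse cells are a weaker argument. The current protocol, already revised for 50-55 patients, keeps the duration stratum, and its scheme has fewer cells than the SAP's.

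A reader might go further in two ways that the documents do not support.

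- **A ribavirin difference cannot be interpreted.** The SAP shows non-cirrhotic 3DAA patients with and without ribavirin side by side. The background trials gave ribavirin for 12 weeks in non-cirrhotic genotype 1 and in genotype 4. Ribavirin use is not equated with a long course.
- **Comparison with the 12-week trials is lost.** The figures in protocol Table 1 are SVR12 rates. The protocol gives no adverse event percentages for the regimen to compare with.

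**Conclusion.** The contradiction between protocol and SAP is explicit, undeclared and needs no assumption. It follows directly that any SAP column holding both courses reports a percentage over mixed windows of about 114 and 198 days. That a cirrhotic versus non-cirrhotic difference may partly reflect duration is an inference, supported by the protocol's own link between duration and disease status.

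Its size cannot be fixed from the documents. Under a constant hazard, non-cirrhotic patients all on 12 weeks and a common 20%, the apparent cirrhotic figure runs from 20% (nobody on 24 weeks, or all events early) to 32.1% (every cirrhotic patient on 24 weeks). The 32.1% is the upper end of that scenario, not an expected effect. The SVR12 estimate is untouched. The SAP should be corrected, but the consequence is limited to how tolerability is read. The table shells in Part II of the SAP are not among the documents reviewed.

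**What to change.** - In SAP 4.2.8.3 and Table 11, add a set by regimen and scheduled duration (12 versus 24 weeks) for the main treatment-emergent tables: all events, serious events, severity, relatedness and withdrawal. Define the matching groups in 4.2.1.
- Keep the regimen-by-cirrhosis tables as a separate set, not crossed with duration.
- In the pooled and cirrhosis columns, add either events per 100 patient-weeks or the percentage of patients with onset in the first 12 weeks of treatment. Count events with missing onset separately. A cut-off at day 114 would not serve: it covers 84 days on treatment plus 30 off for one course and 114 days on treatment for the other.
- State in the SAP that the cirrhosis stratification is an addition to the protocol, with the reason.

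The cost is a few extra tables. Planned duration is already an SVR12 covariate in SAP 4.2.7.2.1, and the existing event and exposure definitions already require onset and dosing dates. The drawback is small cells, about 6-7 patients on average across the protocol's 8.
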